8.3. Exploratory Efficacy Analyses

The protocol calls for a Log-Rank test at the 5% two-sided level of significance for the following exploratory outcome measures:

- Time from randomization to initial clinical improvement in Norovirus disease through 28 and 180 days for at least 48 hours.
- Time from randomization to initial cessation of vomiting through Day 180 (recurrent vomiting will be considered disease recurrence unless determined to be due to another etiology [i.e. GVHD]).
- Time from randomization to subject report of no loss of appetite that is maintained for 48 hours through Day 180 (measure will be first time that the subject reports that they have no “loss of appetite” on their daily diary).
- Time from randomization to initial cessation of diarrhea through Day 180 classified by the Bristol Stool Chart as type 6 or 7 bowel movements (recurrent diarrhea will be considered disease recurrence unless determined to be due to another etiology [i.e. GVHD]).
- Time from randomization to 50% reduction in the amount of antimotility agents utilized by the subject through Day 180.

However, due to early closure of the study, the number of subjects is too small to use a Log-Rank test. Instead, a stratified Cox proportional hazards model will be used to compare treatment to control through Day 28 and/or Day 180. Stratification is based on acute versus chronic symptoms at baseline. No pediatric subjects were enrolled in the study and only one hematopoietic stem cell transplant subject was enrolled in the study; therefore, the transplant type and age range strata will not be included in the final analysis.

The analysis will be performed in the mITT analysis population. The treatment hazard ratio estimate, 95% confidence interval and p-value from the likelihood ratio test will be presented for each event (Table 29). The median time to event and 95% confidence interval will be summarized by treatment arm and duration of symptoms. In addition, stratum-specific estimates of the treatment hazard ratio within each duration of symptoms strata will be presented. Kaplan-Meier curves for each treatment arm will be displayed in Figure 20, Figure 21, Figure 22, Figure 23, and Figure 24.

The protocol calls for two-sample t-tests to be used for the below outcome measures. However, due to early closure of the study, the number of subjects is too small to meet the normality assumptions of the t-test; therefore Wilcoxon-Mann-Whitney exact rank sum tests will be used to compare treatment to placebo through Day 28 and/or Day 180 in the mITT analysis population (Table 30) for the following outcome measures (defined in Section 3.3):

- Number of days of diarrhea through Days 28 and 180.
- Number of stools classified by the Bristol Stool Chart as type 6 or 7 bowel movements through Day 28.
- Number of days of IV hydration or total parenteral nutrition (TPN) therapy through Day 28.

The following patient-reported outcome measures will be assessed using ANCOVA adjusting for the baseline patient-reported measure:

- Change in patient-reported quality of life as measured by EuroQOL-5 (global) and IBSQOL (diarrhea specific) [adult] or Euro QOL-5 Peds (global) and PedsQL GI Module [children] from baseline to Day 180.
- Change in patient-reported physical function as measured by the NIH PROMIS Physical Function (Adult) Pediatric Global Health (Peds) from baseline to Day 180.
- Change in patient-reported emotional distress as measured by the NIH PROMIS Depression, Anxiety, Fatigue (Adult and Peds) from baseline to Day 180.
- Change in patient-reported gastrointestinal symptoms as measured by the NIH PROMIS GI (Adult and Peds) symptoms (6 of 8 subscales) from baseline to Day 180.

The analysis will be conducted in the mITT population. [Table 31](#) and [Table 32](#) will present the frequency of reported problems the EuroQOL-5 quality of life by dimension and study day for the nitazoxanide and placebo groups, respectively. [Table 33](#) will present the observed means and standard deviations of the change in each patient-reported measure between baseline and Day 180 for each treatment group. Levene's test and normality checks will be carried out to check if the assumptions of ANCOVA are met. If assumptions of ANCOVA have been met, the adjusted mean, standard error, and 95% confidence intervals for each treatment group. The p-value for the test of between-treatment differences will also be presented. If the assumptions of ANCOVA are not met, transformations of the change in patient-reported measure variable may be utilized to correct any skewness in residuals or heterogeneity of the variances. If a transformation of the dependent variable is used, a footnote in the table will denote which transformation was used in the analyses for each patient-reported measure. If the assumptions of ANCOVA cannot be met through transformation of the dependent variable, only the observed mean, standard deviation and 95% confidence intervals of the unadjusted change in patient-reported measure and study day will be reported. The protocol also calls for pairwise contrasts between groups on the unadjusted change between baseline and subsequent timepoints and on adjusted change (controlling for baseline) using a mixed-design analysis of variance (ANOVA) model with all times, including baseline, as a repeated measures factor. However, due to early closure of the study, the number of subjects is too small to provide adequate power for any multiple comparison tests. Instead, [Table 33](#) will present the observed means and standard deviations of the change in each patient-reported measure between baseline and Days 28, 60, and 120 for each treatment group. Since a single index is not currently possible for the EuroQOL-5 questionnaire, these results will not be included in [Table 33](#). If ANCOVA assumptions are met, the adjusted mean, standard error, and 95% confidence intervals for each treatment group and study day will also be presented.

The effect of co-pathogens, as determined by the BioFire stool pathogen screen, on the primary outcome measure is presented in [Table 34](#), where the presence or absence of co-pathogens will be represented as a binary covariate in the Cox proportional hazards model. If it is determined that subjects' co-pathogen status changes often throughout the study, the effect of co-pathogens will be a time-varying covariate instead of a binary covariate.

Time from randomization until clinical resolution of Norovirus symptoms for at least 48 hours through Day 180. Clinical resolution will be assessed from the daily diary by the subject and will be defined as cessation of vomiting and no stools classified by the Bristol Stool Chart as diarrhea (Type 6 or 7) from the total population compared to the subgroup of subjects who do not report chromaturia (discoloration of urine) based on unsolicited self-reporting is presented in [Table 18](#).

The effect of co-pathogens, as determined by the BioFire stool pathogen screen, on the time from randomization to first negative viral load through 180 days is presented in [Table 35](#) and [Table 36](#) for Norovirus GII and Norovirus GI test types, respectively, where the presence or absence of co-pathogens will be represented as a binary covariate in the Cox proportional hazards model. If it is determined that subjects' co-pathogen status changes often throughout the study, the effect of co-pathogens will be a time-varying covariate instead of a binary covariate.

Time from the randomization to first negative viral load through 180 days and the change in viral titer between Day 1 and 180 from the total population compared to the subgroup of subjects who do not report chromaturia (discoloration of urine) based on unsolicited self-reporting will be presented in [Table 23](#) and [Table 24](#) for Norovirus GII and Norovirus GI test types, respectively .

Analyses of the following exploratory outcome measures are not covered in this SAP:

- Time to ≥ 1 log reduction in stool Norovirus genome copies
- Change in quantitative Norovirus load in the stool between Day 1 and Day 7, 14, 21, 28, 60, 120, and 180.
- Change in Norovirus sequence from Day 1 to Days 28 and 60.

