5.1 Subject Inclusion Criteria

Subjects should meet all of the following inclusion criteria

1. Male or female age ≥ 12 years.
2. Recipient of a solid organ or hematopoietic stem cell transplant.
3. Positive test result for Norovirus within 14 days of enrollment that is obtained as part of routine clinical care using a Norovirus testing available to the site.
4. Active GI symptoms (diarrhea or vomiting) that, in the opinion of the PI, are secondary to Norovirus.[#]
5. Willing and able to provide written informed consent and assent before initiation of any study procedures, consistent with local IRB policy.
6. Subjects must be of non-childbearing potential or if of childbearing potential, must be using an effective method of birth control or must be abstinent.
 - Non-childbearing potential is defined as surgically sterile or postmenopausal for $>$ one year.
 - Effective methods of birth control include the use of hormonal or barrier birth control such as implants, injectable contraceptives, combined oral contraceptives, intrauterine devices [IUDs] or condoms with spermicidal agents during study period. Female subjects must be using an effective method of birth control or practice abstinence and must agree to continue such precautions during the study and for 30 days after the Day 28 study visit.
 - A woman is eligible if she is monogamous with a vasectomized male. This subject is considered low risk and not required to use contraception.
7. Agrees to complete all screening requirements, study visits and procedures.

[#] Patients must have active diarrhea, which is defined as at least 3 days of Bristol 6 or 7 stools in the past 2 weeks prior to enrollment per patient report.

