3.3. Study Definitions and Derived Variables

Diarrhea:

Diarrhea will be defined as Type 6 or 7 on the Bristol Stool chart.

Baseline Value:

The baseline value will be defined as the last value obtained prior to the first dose of study product unless otherwise noted.

Additional Nitazoxanide:

Any nitazoxanide reported as a concomitant medication will be considered additional nitazoxanide.

Initial Clinical Resolution of Norovirus Symptoms:

Clinical resolution of Norovirus symptoms will be assessed from the daily diary by the subject and will be defined as:

- Cessation of vomiting and,
- No stools classified by the Bristol Stool Chart as diarrhea (Type 6 or 7).

Subjects will need to have at least two consecutive daily diary entries where they reported no vomiting, no Bristol Stool Type 6, and no Bristol Stool Type 7 to meet the criteria for initial clinical resolution. There are several variables in the daily diary that indicate whether the subject had diarrhea or vomiting for that day.

Daily Diary Diarrhea Questions:

- Phase 1 (Treatment Phase):
 - Number of Bristol Type 6 stools? (Quantitative)
 - Were there too many Bristol Type 6 stools to count? (Qualitative)
 - Number of Bristol Type 7 stools? (Quantitative)
 - Were there too many Bristol Type 7 stools to count? (Qualitative)
- Phase 2 (Longitudinal Phase):
 - Did you have diarrhea today? (By diarrhea, we mean at least ONE bowel movement that could be described as Type 6 or 7.) (Qualitative)

Daily Diary Vomiting Questions:

- Phase 1 (Treatment Phase):
 - Did you have to take another dose because you threw up the first dose within 1 hour? (Qualitative)
 - How many times did you vomit today? (Quantitative)
- Phase 2 (Longitudinal Phase):
 - Did you vomit today? (Qualitative)

For a day to count towards clinical resolution during the treatment phase, the following responses must be recorded in the daily diary entry:

- Both quantitative diarrhea questions must be 0

- Both qualitative diarrhea questions must be missing (i.e. not “yes”)
- The quantitative vomiting questions must be 0
- The qualitative vomiting question must be “no”

For a day to count towards clinical resolution during the longitudinal phase, the following responses must be recorded in the daily diary entry:

- The qualitative diarrhea question must be “no”
- The quantitative vomiting question must be 0

If a daily diary entry is missing, refer to the imputation rules in Section [6.5](#).

Viral Load:

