4.3. Selection of Study Population

All candidates at all centers who meet all eligibility requirements will be offered the opportunity to participate in the trial. Study subjects are seen in patient or clinic setting and have either community onset or hospital acquired disease.

Inclusion Criteria

Subjects should meet all of the following inclusion criteria:

1. Male or female age ≥ 12 years.
2. Recipient of a solid organ or hematopoietic stem cell transplant.
3. Positive test result for Norovirus within 14 days of enrollment that is obtained as part of routine clinical care using a Norovirus testing available to the site.
4. Active GI symptoms (diarrhea or vomiting) that, in the opinion of the PI, are secondary to Norovirus.[#]
Patients must have active diarrhea, which is defined as at least 3 days of Bristol 6 or 7 stools in the past 2 weeks prior to enrollment per patient report.
5. Willing and able to provide written informed consent and assent before initiation of any study procedures, consistent with local IRB policy.

6. Subjects must be of non-childbearing potential or if of childbearing potential, must be using an effective method of birth control or must be abstinent.
 - Non-childbearing potential is defined as surgically sterile or postmenopausal for > one year.
 - Effective methods of birth control include the use of hormonal or barrier birth control such as implants, injectable contraceptives, combined oral contraceptives, intrauterine devices [IUDs] or condoms with spermicidal agents during study period. Female subjects must be using an effective method of birth control or practice abstinence and must agree to continue such precautions during the study and for 30 days after the Day 28 study visit.
 - A woman is eligible if she is monogamous with a vasectomized male. This subject is considered low risk and not required to use contraception.
7. Agrees to complete all screening requirements, study visits and procedures.

Exclusion Criteria:

Subjects meeting any of the following exclusion criteria at baseline will be excluded from study participation:

1. Other identified infectious causes of diarrhea at screening*.

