6.3.1. Modified Intention-to-Treat (mITT) Population

The mITT population includes all randomized subjects who received at least one dose of assigned study drug. Analyses are performed according to randomized treatment assignment, not the treatment received. This analysis set will be used for all efficacy analyses and will be considered the primary analysis for the primary efficacy outcome measure.

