Table 28: Change in Viral Titer between Day 1 and Day 180 by Treatment Group and Duration of Symptoms: Subgroup Sensitivity Analysis – Norovirus GI, mITT Population

Table 29: Exploratory Time to Event by Treatment Group and Duration of Symptoms – mITT Population

Implementation Note: If an estimate is not calculable, insert “NC” in the cell and add a footnote “NC = Not calculable.” If a subgroup has less than 5 subjects per treatment group, then remove rows and add footnote specifying which group(s) are excluded from analyses.

Event	Treatment Group	Duration of Symptoms	n	Median Time to Event		HR		P-value
				Estimate	95% CI	Estimate	95% CI	
Clinical Improvement (Day 28)	Nitazoxanide 500 mg (N=X)	Acute	x	x.x	x.x, x.x	x.xx	x.xx, x.xx	--
	Placebo (N=X)		x	x.x	x.x, x.x			
	Nitazoxanide 500 mg (N=X)	Chronic	x	x.x	x.x, x.x	x.xx	x.xx, x.xx	--
	Placebo (N=X)		x	x.x	x.x, x.x			
	Nitazoxanide 500 mg (N=X)	Any Duration	x	x.x	x.x, x.x	x.xx	x.xx, x.xx	0.xxx
	Placebo (N=X)		x	x.x	x.x, x.x			
Clinical Improvement (Day 180)	Nitazoxanide 500 mg (N=X)	Acute	x	x.x	x.x, x.x	x.xx	x.xx, x.xx	--
	Placebo (N=X)		x	x.x	x.x, x.x			
	Nitazoxanide 500 mg (N=X)	Chronic	x	x.x	x.x, x.x	x.xx	x.xx, x.xx	--
	Placebo (N=X)		x	x.x	x.x, x.x			
	Nitazoxanide 500 mg (N=X)	Any Duration	x	x.x	x.x, x.x	x.xx	x.xx, x.xx	0.xxx
	Placebo (N=X)		x	x.x	x.x, x.x			

Repeat for Cessation of Vomiting, No Loss of Appetite, Cessation of Diarrhea, and 50% Reduction in Antimotility Agents

N = Number of subjects in the specified treatment group, duration of symptoms strata, and analysis population.

n = Number of subjects with initial clinical resolution of symptoms.

Note: HR is the ratio of the hazard of the given event in each treatment group estimated from the Cox model. The ratio is Nitazoxanide 500 mg to Placebo.

HR for the ‘Any Duration’ group is the hazard ratio from the stratified Cox Model.

P-value calculated using the likelihood ratio test.

Table 30: Exploratory Summary Statistics of Clinical Improvement Measures by Treatment Group – mITT Population

Clinical Improvement Measure	Statistic	Nitazoxanide 500 mg (N=X)	Placebo (N=X)
Days of Diarrhea (Day 28)	Mean	X.X	X.X
	Median	X.X	X.X
	Standard Deviation	X.X	X.X
	Minimum	X	X
	Maximum	X	X
	P-value ^a		0.xxx
Days of Diarrhea (Day 180)	Mean	X.X	X.X
	Median	X.X	X.X
	Standard Deviation	X.X	X.X
	Minimum	X	X
	Maximum	X	X
	P-value ^a		0.xxx

Implementation note: Repeat for Number of Type 6 or 7 stools and Days of IV Hydration/TPN Therapy

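### Time to cessation of vomiting, and time to no loss of appetite, are analysed in all mITT subjects although entry requires neither symptom, and neither the event nor the at-risk set is defined

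*SAP*

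**What the plan says.** SAP 8.3 lists five exploratory time-to-event outcomes. Two concern us: "Time from randomization to initial cessation of vomiting through Day 180", and the time to a report of no loss of appetite that is kept up for 48 hours. Both are compared by a Cox model stratified by acute or chronic symptoms, and "The analysis will be performed in the mITT analysis population". SAP 6.3.1 gives that population: "The mITT population includes all randomized subjects who received at least one dose of assigned study drug". Symptoms at baseline play no part in it.

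On entry, SAP 4.3 asks for "Active GI symptoms (diarrhea or vomiting) that, in the opinion of the PI, are secondary to Norovirus". The footnote to the same criterion in Protocol 5.1 makes diarrhea compulsory: "Patients must have active diarrhea, which is defined as at least 3 days of Bristol 6 or 7 stools in the past 2 weeks". Vomiting is therefore not needed for entry, and neither is loss of appetite. The symptom list used for stratification (Protocol 5.3.1) omits vomiting and offers abnormal appetite only as one alternative.

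SAP 3.3 derives clinical resolution, clinical improvement, antimotility reduction and days of diarrhea. It derives neither cessation of vomiting nor return of appetite. The Table 29 shell, to be repeated for both outcomes, defines its denominator as "N = Number of subjects in the specified treatment group, duration of symptoms strata, and analysis population".

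For viral load the SAP takes a different course. SAP 3.3 excludes subjects who were not positive at baseline, and the Table 21 denominator counts only those who were.

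**The concern.** A time-to-cessation outcome has meaning only for a subject who has something to cease. With all mITT subjects in the risk set, those who never vomited must be given some outcome, and the SAP does not say which. The treatment-phase diary records a daily count of vomiting episodes and the vomiting outcome has no 48-hour condition, so a never-vomiter who enters zero on the first diary meets it at once.

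That puts a block of tied events at the first diary day in both arms, carrying no information about treatment. The hazard ratio is pulled toward 1. If the block is large, the median and the Kaplan-Meier curve describe the case mix at entry and not recovery. The appetite outcome has the same structural gap, although its 48-hour condition means that one clean entry does not suffice.

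**Working it through.** **No stated figure to reproduce.** The documents give no sample size, power or rate for either outcome.

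**Inputs from the documents.** 1:1 allocation (SAP 4.4.3); 31 subjects enrolled (SAP 14.2); Cox model stratified by acute or chronic symptoms, with tie handling not stated (SAP 8.3); follow-up to Day 180.

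**Assumptions that are not in the documents.** Never-vomiter share 25% to 75%, equal in both arms; hazard ratio among vomiters 1.5, 2.0 or 3.0; placebo median time to cessation 7 or 14 days.

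**Why the estimate shrinks.** Suppose d never-vomiters, split evenly between arms, are events on the first day, when the arms at risk are of equal size. With Breslow ties, their contribution to the score at hazard ratio θ is d × [1/2 − θ/(1+θ)]. At θ = 2 this is d × (1/2 − 2/3) = −d/6, and it is zero only at θ = 1. The block pulls the estimate toward 1, more strongly the larger d is.

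**Never-vomiters as events on the first day** (simulated stratified Cox model, Efron ties, placebo median 7 days), estimated hazard ratio:

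| True hazard ratio among vomiters | 0% never vomit | 25% | 50% | 75% |
|---|---|---|---|---|
| 1.5 | 1.48 | 1.34 | 1.21 | 1.08 |
| 2.0 | 2.04 | 1.66 | 1.37 | 1.18 |
| 3.0 | 3.05 | 2.25 | 1.63 | 1.25 |

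A separate simulation with Breslow ties, a 14-day placebo median and true hazard ratio 2.0 gave 1.59, 1.37 and 1.21 at 30%, 50% and 70%. A repeat under the same settings gave 1.58, 1.37 and 1.19.

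**At 31 subjects, true hazard ratio 2.0.** The median estimate is 2.06, 1.57, 1.36 and 1.13 at 0%, 25%, 50% and 75%. Rejection by the Wald test falls from about 40% to 19%, 10% and 3%.

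**Never-vomiters censored at Day 180 instead.** A hazard ratio of 2.0 becomes 1.27, 1.14 and 1.06 at 25%, 50% and 75%. Dilution does not depend on the first-diary reading, and is greater under this one.

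**Restricted to vomiters.** At 31 subjects the median estimate is 1.97 and 1.94 at 25% and 50% never-vomiters. At 75% too few vomiters remain for a stable fit.

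**Median time.** If at least half the subjects are events at the first diary, the Kaplan-Meier estimate is at or below 0.5 on that day, so the median is that day whatever the vomiters do.

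**No treatment effect.** The hazard ratio stays near 1 and rejection near 5%.

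**Size of the restricted risk set.** 31/2 = 15.5 per arm. At 30%, 50% and 70% never-vomiters this leaves 15.5 × 0.7 = 10.9, 15.5 × 0.5 = 7.8 and 15.5 × 0.3 = 4.7 per arm, before the acute/chronic split.

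**The case against.** The strongest reply is that the SAP contains no rule scoring never-vomiters as first-day events. That is right. A reader might infer such a rule from the diary item and the outcome wording, but because SAP 3.3 leaves the event undefined, a programmer could also censor these subjects or drop them. The defect is therefore an undefined event and at-risk set in a stated all-mITT analysis. It still matters, because both ways of keeping never-vomiters in that population dilute the hazard ratio. Only exclusion avoids this, and the SAP does not provide for it.

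A reader might also want to state the loss as power in the planned 160 subjects. That figure should not be used. In reruns at 160 subjects with 30%, 50% and 70% never-vomiters, rejection was 82%, 47% and 6% with Breslow ties, 83%, 55% and 18% with Efron ties, and 86%, 69% and 40% with an ordinary log-rank test. Much of the apparent collapse comes from the tie method, which the SAP does not state, and a trial of 160 will not be analysed. At 31 subjects power is low either way: restriction to vomiters gives about 34%, 25% and 18% by likelihood ratio test at the same shares.

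It would also go too far to carry the vomiting figures over to appetite. That outcome was not simulated, and its 48-hour condition changes when the event occurs. The same gap in definition holds for it; the same size has not been shown.

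Finally, these are two of five exploratory time-to-event outcomes in a SAP that expects its analyses to be mainly descriptive. That stands, and it limits the weight of the point.

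**Conclusion.** The point holds as a minor one. The stated population, the Table 29 denominator and the absence of any event definition together put subjects without the symptom into an analysis of its cessation. If the hazard ratio among vomiters is 2.0 and the placebo median 7 to 14 days, scoring never-vomiters at the first diary gives about 1.6-1.7, 1.4 and 1.2 at 25-30%, 50% and 70-75% never-vomiters, with similar values at 31 subjects. From 50% upward the median time is simply the first diary day. These sizes rest on assumed inputs; the never-vomiter share in particular is not in the documents.

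The harm is attenuation and a median that cannot be interpreted. A reader might infer false positives or damage to the main conclusion, but rejection under no effect stays near 5%, and neither the primary nor the secondary outcomes use these derivations. With 31 subjects, chance imbalance of never-vomiters between arms could also move the estimate in either direction.

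**What to change.** Define both events in SAP 3.3 and restrict each analysis to subjects at risk, as is already done for viral load.

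- **Vomiting:** mITT subjects with vomiting at baseline, from one stated source. The Day 1 Weekly Recall (average vomiting episodes per day, held in Listing 14) is one choice. The first non-missing diary, which SAP 3.3 already uses for clinical improvement, is the other. The Recall would differ from the clinical-improvement baseline. The diary may be post-dose, since SAP 4.5.1 starts it at dispensation and Protocol 7.1 gives the first dose at that visit.
- **Appetite:** mITT subjects reporting loss of appetite on the first non-missing diary, with a note that this entry may be post-dose.
- **Outputs:** change N in Table 29 and Figures 21 and 22 to the number at risk by arm. Apply the SAP 8 rule on fewer than five subjects per treatment group to these sets, and give descriptive results only where it bites.

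The cost is SAP wording and shell changes, with no new data. The price is smaller risk sets: on the arithmetic above, about 8 per arm if half never vomited, and below five at 70%.
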